13.2 Adverse Events

| Term | Definition |
|---|--|
| Adverse Event (AE) | An adverse event is defined as any untoward medical occurrence in a subject administered a pharmaceutical product, which does not necessarily have a causal relationship with this treatment. An AE can therefore be any unfavorable and/or unintended sign (including an abnormal laboratory finding), symptom, or disease temporally associated with the use of an investigational medicinal product, whether or not related to the investigational medicinal product. |
| Treatment-emergent Adverse Event (TEAE) | A treatment-emergent adverse event is an event that emerges during treatment having been absent pre-treatment, or worsens relative to the pre-treatment state. |
| Causality Assessment | The relationship of an AE to the administration of the study drug is to be assessed according to the following definitions: 
 - No (unrelated, not related, no relation) – The time course between the administration of study drug and the occurrence or worsening of the AE rules out a causal relationship and another cause (concomitant drugs, therapies, complications, etc.) is suspected. - Yes (related) – The time course between the administration of study drug and the occurrence or worsening of the AE is consistent with a causal relationship and no other cause (concomitant drugs, therapies, complications, etc.) can be identified. |
| Related TEAE | A related treatment-emergent adverse event is a treatment-emergent adverse event whose Investigator causality assessment is related. |

| | |
|---|---|
| Serious TEAE/ Serious Related TEAE | 
A serious TEAE is a treatment-emergent adverse event which is considered serious if, in the view of either the Investigator or Sponsor, it results in any of the following outcomes:
 
 - Death - A life-threatening adverse event - Requires hospitalization or prolongation of existing hospitalization - A persistent or significant disability/incapacity or substantial disruption of the ability to conduct normal life functions - A congenital anomaly/birth defect - An important medical event 
A serious related TEAE is a serious TEAE whose Investigator causality assessment is related.
 |
| TEAE of Special Interest (TEAESI)/Related TEAESI | 
TEAE of Special Interest (TEAESI) is a treatment-emergent adverse event which meets the following descriptions:
 
 - Thromboembolic events include the adverse events with MedDRA PT belonging to Standard MedDRA Queries (SMQ Narrow PTs) 'Embolic and thrombotic events'. - Bleeding events include the adverse events with MedDRA PT belonging to 2nd level SMQ (Narrow PTs) 'Haemorrhage terms (excl laboratory terms)' with CTCAE Grades 3 and 4. 
A related TEAESI is a TEAESI whose Investigator causality assessment is related.
 |
| Adverse Event Severity | 
The severity of all AEs should be graded according to the Common Terminology Criteria for Adverse Events Version 5.0 (CTCAE). For those AEs not listed in the CTCAE, the following grading system should be used:
 
 - Mild (CTCAE Grade 1): Transient symptoms, awareness of sign/symptom, but easily tolerated and no interference with subject's daily activities. - Moderate (CTCAE Grade 2): Marked signs/symptoms that interfere with subject's usual activities, but still acceptable. - Severe (CTCAE Grade 3): Incapacitating signs/symptoms which cause considerable interference with the subject's daily activities, unacceptable. - Life-threatening (CTCAE Grade 4): Life-threatening or disabling AE. - Death (CTCAE Grade 5): Death-related AE. |

The data handling methods for Adverse Events are presented below:

Only TEAEs will be tabulated in the tables. Non-TEAEs are only included in the listings.

- Number of Subjects with Multiple Events:
- For overview summary:
 - If multiple AEs occurred in the same subject, the subject will only be counted once.

- If AEs with multiple grades occurred in the same subject, the subject will be counted once in the highest reported grade.
- For summary by SOC and PT:
 - If multiple AEs of same SOC or PT occurred in the same subject, the subject will only be counted once in the SOC or PT.
 - If multiple AEs of same SOC or PT with different grades occurred in the same subject, the subject will be counted once in the highest reported grade.
- For summary by PT:
 - If multiple AEs of same PT occurred in the same subject, the subject will only be counted once in the PT.
- For summary by AESI category and PT:
 - If multiple AEs of same AESI category or PT occurred in the same subject, the subject will only be counted once in the AESI category or PT.

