# 9.1.2 Adverse Events of Special Interest

The Investigator will monitor each subject for clinical and laboratory evidence for pre-defined AEs of special interest (AESI) throughout their participation in this study. The purpose for specifying these AESI is to enable further characterization of the clinical course and management of these events. An AESI may or may not be the consequence of treatment with avatrombopag.

The AESI defined in this protocol include:

- Thromboembolic events (any thrombotic or embolic event, whether arterial or venous); and
- Bleeding events (WHO Grades 3 and 4).

These events will be recorded in the AE eCRF page. The Investigator will assess and record any additional information on the AESI in detail on a SAE form (whether or not the event meets seriousness criteria in Section 9.3), to be submitted within 24 hours of awareness of the event. During the course of the study, additional AESI may be identified by the Sponsor.

Efficacy endpoints, as described in Section 3, should not be reported as AEs unless in the opinion of the Investigator the event is causally associated with the study drug. For example, thrombocytopenia or platelet transfusions for thrombocytopenia should not be reported as AEs; however, clinically significant bleeding events should always be reported as AESIs.

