# APPENDIX C: WHO BLEEDING SCALE

Grade 0	No bleeding
Grade 1	Petechial bleeding
Grade 2	Mild blood loss (clinically significant)
Grade 3	Gross blood loss
Grade 4	Debilitating blood loss

a: Fogarty, 2012; Miller, 1981

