5.1 Changes from Planned Analyses in the Protocol

A secondary efficacy endpoint was included which was not detailed in the protocol: Proportion of subjects with a reduction in use of concomitant ITP medications from baseline.

Bleeding Adverse Events of Special Interest (AESIs) were first identified using a Standardised Medical Dictionary for Regulatory Activities Query (MedDRA SMQ) and then further defined as clinically significant using reported Common Terminology Criteria for Adverse Events (CTCAE) grade for the event rather than the WHO bleeding grade, as WHO bleeding grades collected at study visits are not linked to specific adverse events.

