13.2.1 Overview of Treatment-emergent Adverse Events

Population: Safety Set

Target Phases: Core Phase, Core Phase and Extension Phase

Analysis items: - TEAEs, Related TEAEs, Serious TEAEs, Serious Related TEAEs, TEAEs by maximum severity (Grade 1, Grade 2, Grade 3, Grade 4, Grade 5, Grade ≥ 3), TEAEs of Special Interest (Thromboembolic events, Bleeding events (CTCAE Grades 3 and 4)), Related TEAEs of Special Interest, TEAEs leading to death

Contents: - The number of events and the number and proportion of subjects who experienced at least 1 event in the Analysis items are calculated.

Definitions: - The denominator to calculate the proportion is the target population.

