13.2.2 Overview of Treatment-emergent Adverse Events by Subgroups

Population: Safety Set

Target Phases: Core Phase, Core Phase and Extension Phase

Analysis items: - TEAEs, Related TEAEs, Serious TEAEs, Serious Related TEAEs, TEAEs by maximum severity (Grade 1, Grade 2, Grade 3, Grade 4, Grade 5, Grade ≥ 3), TEAEs of Special Interest (Thromboembolic events, Bleeding events (CTCAE Grades 3 and 4)), Related TEAEs of Special Interest, TEAEs leading to death

Contents: - Conduct a subgroup analysis for "[13.2.1 Overview of Treatment-emergent Adverse Events](#)". Subgroups are below:

- Sex (Male, Female)
- Age (<65 yrs, ≥ 65 yrs)

- Baseline platelet count ($\leq 15 \times 10^9 / L$, $> 15 \times 10^9 / L$)
- Use of concomitant ITP medications (Yes, No)
- Splenectomy status (Yes, No)
- Baseline creatinine clearance ($30 \leq - < 60 \text{ mL/min}$, $60 \leq - < 90 \text{ mL/min}$, $\geq 90 \text{ mL/min}$, Missing (if any))

Definitions: - The denominator to calculate the proportion is the number of subjects in each subgroup.

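### Bleeding AESIs are limited to CTCAE Grades 3 and 4, so a haemorrhage recorded only as Grade 5 (death) is left out of the AESI counts

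*SAP*

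**What the plan says.** Protocol 9.1.2 names two AESI categories. One is any thromboembolic event; the other is "Bleeding events (WHO Grades 3 and 4"). The same section says that clinically significant bleeding is always to be reported as an AESI. In Protocol Appendix C the WHO scale runs from Grade 0 to Grade 4, and Grade 4 is "Debilitating blood loss".

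SAP 5.1 declares a change. Bleeding AESIs are first found by a MedDRA query and then classed as clinically significant by the CTCAE "grade for the event rather than the WHO bleeding grade". The reason given is that WHO grades taken at visits are not tied to individual adverse events.

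SAP 13.2 puts this into effect by taking narrow haemorrhage terms "with CTCAE Grades 3 and 4". The severity row of the same table ends with "Death (CTCAE Grade 5): Death-related AE". The thromboembolic category is defined by query terms alone ("Thromboembolic events include the adverse events with MedDRA PT belonging to Standard MedDRA Queries", narrow terms) with no grade condition. The label "Bleeding events (CTCAE Grades 3 and 4") appears in 13.2.1 and is repeated in 13.2.2 and 13.2.4.

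**The concern.** On the WHO scale, 3 and 4 means Grade 3 or worse, because nothing lies above 4. On CTCAE the same two numbers form a closed range that stops one grade short of the top. The wording was carried over while its meaning changed, and the most severe outcome dropped out of the category.

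SAP 5.1 explains why the scale was changed. It does not mention the loss of the top grade or give a reason for it. The result also works against the SAP's own purpose: a rule meant to pick out clinically significant bleeding excludes fatal bleeding.

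Bleeding is one of only two pre-defined AESI categories, and safety is a secondary objective of the Core Phase and the primary objective of the Extension Phase. A fatal bleed that the investigator reported as an AESI under Protocol 9.1.2 could be absent from the AESI tables. Someone reading the two categories side by side would not know that fatal events are handled differently in each.

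**Working it through.** The plan states no figure to reproduce here. The check is to apply the grade rule to each grade and then trace the outputs that use it.

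**Step 1. Grade rule.** Inputs: the filter in SAP 13.2 (Grades 3 and 4), the CTCAE grades 1 to 5 in the severity row of the same table, and the alternative filter of Grade 3 or higher.

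| CTCAE grade | SAP filter {3, 4} | Grade 3 or higher |
|---|---|---|
| 1 | out | out |
| 2 | out | out |
| 3 | in | in |
| 4 | in | in |
| 5 (death) | **out** | **in** |

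Grade 5 is the only grade on which the two rules differ.

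**Step 2. The same numbers on the protocol's scale.** The WHO grades in Appendix C are 0 to 4. On that scale {3, 4} and Grade 3 or higher select the same events, so the gap arises only on the move to CTCAE.

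**Step 3. Outputs affected.**
- SAP 13.2.1 (overview): bleeding AESI events and subjects, and the related-AESI row if the event is judged related.
- SAP 13.2.2 (overview by subgroup): the same items.
- SAP 13.2.4 (AESI category and preferred term): subjects.
- Listing 14.3.2.3 (treatment-emergent AESIs): by inference, since SAP 14 states no filter of its own and the listing uses the defined term.

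**Step 4. Outputs not affected.** The event stays in the Grade 5 and Grade ≥3 severity rows, the serious rows and the row for events leading to death in 13.2.1. It also stays in the tables by system organ class and preferred term (13.2.3 and 13.2.7) and in listings 14.3.2.1 and 14.3.2.2.

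**Step 5. Size, as an illustration.** Assume one subject with a haemorrhage recorded only as Grade 5 and no other bleeding AESI. SAP 4.2 plans at least 19 subjects, so take an assumed Safety Set of 19 to 25; the upper figure is ours, not the plan's.

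| Safety Set (assumed) | SAP filter | Grade 3 or higher |
|---|---|---|
| 19 | 0/19 = 0% | 1/19 = 5.3% |
| 25 | 0/25 = 0% | 1/25 = 4.0% |

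The event count in 13.2.1 is 0 instead of 1. For scale, the exact 95% interval is 0 to 17.6% for 0/19 and 0.1 to 26.0% for 1/19. These percentages do not carry over to 13.2.2, where "The denominator to calculate the proportion is the number of subjects in each subgroup".

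**The case against.** The strongest reply is that little would be hidden. A fatal bleed in a single-arm study of about 19 subjects would be seen by any reader, and the very overview table that omits it from the bleeding row also has a Grade 5 row and a row for events leading to death. The AESI outputs are descriptive, and no test or efficacy result depends on them. This stands, and it limits the weight of the point.

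The consequence is also conditional. It needs a treatment-emergent fatal haemorrhage coded to a narrow query term, in a subject with no separate Grade 3 or 4 bleeding record. If there is such a record, the subject is still counted. The documents do not say how worsening events are recorded and give no basis for a probability. This stands too, so the figures above show what one event would do and are not a forecast.

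The two AESI categories already differed in the protocol, where only bleeding is limited by grade. That is correct; what the SAP adds is the unequal treatment of fatal events.

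Finally, Grade 3 or higher would not restore full agreement with AESIs reported by investigators, since a bleed of WHO Grade 3 or 4 but CTCAE Grade 1 or 2 would still drop out. That is true, but it follows from the declared change of scale. The loss of Grade 5 is neither declared nor explained.

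None of these replies supplies a reason for leaving fatal bleeds out of the category.

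**Conclusion.** The concern holds. As written, SAP 13.2 excludes a haemorrhage recorded only as CTCAE Grade 5 from the bleeding AESI and related-AESI counts, and nothing elsewhere in the SAP adds it back. The text points to a carry-over from a scale that ended at 4, not to a deliberate choice.

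For a single such event, the bleeding row loses 5.3 percentage points with 19 subjects and 4.0 with 25, and one event disappears from 13.2.1. This assumes no separate Grade 3 or 4 record and no other bleeding AESI. The absence from listing 14.3.2.3 is inferred.

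The effect is confined to AESI tabulation. It should be corrected because an AESI table ought to be complete without cross-checking against the death listing, but it does not threaten the trial's main conclusions.

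**What to change.** In SAP 13.2, keep the same haemorrhage query terms and set the condition to CTCAE Grade ≥3 (Grades 3, 4 and 5). Change the bleeding label in 13.2.1, 13.2.2 and 13.2.4 to match, and state that listing 14.3.2.3 uses the same definition. If leaving out Grade 5 is intended, SAP 5.1 should say so and give the reason.

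The cost is one definition, three labels and one filter condition in the code. No new data are needed, and the events counted at Grades 3 and 4 do not change.

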13.2.1 Overview of Treatment-emergent Adverse Events

Population: Safety Set

Target Phases: Core Phase, Core Phase and Extension Phase

Analysis items: - TEAEs, Related TEAEs, Serious TEAEs, Serious Related TEAEs, TEAEs by maximum severity (Grade 1, Grade 2, Grade 3, Grade 4, Grade 5, Grade ≥ 3), TEAEs of Special Interest (Thromboembolic events, Bleeding events (CTCAE Grades 3 and 4)), Related TEAEs of Special Interest, TEAEs leading to death

Contents: - The number of events and the number and proportion of subjects who experienced at least 1 event in the Analysis items are calculated.

Definitions: - The denominator to calculate the proportion is the target population.

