### 4.4 Extension Phase

Those subjects who meet all the eligibility requirements for the Extension Phase and who are willing and able will enter the Extension Phase and can continue to receive avatrombopag in the Extension Phase until market authorization in Japan. Subjects entering directly into the Extension Phase will not enter the Dose-tapering and Follow-up Periods of the Core Study.

Safety and efficacy data will be collected monthly in the Extension Phase. Subjects who require study drug dose adjustments, who undergo concomitant ITP medication reduction, or who receive rescue therapy during the Extension Phase are required to return for weekly visits for 3 consecutive weeks.

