*: Item “Subjects who are ongoing in the extension phase” only exists in the first analysis (after the last patient completes the Core Phase).

If a subject has multiple discontinuation reasons, they will be counted for each individual discontinuation reason.

Definitions: For each of the following items, the denominator is defined as noted below.
Core Phase

| Items | The denominator of percentage |
|--|--|
| 
 • Enrolled into core phase study • Completed the core phase study • Discontinued the core phase study • Reason for discontinuation • Completed the core phase treatment • Prematurely discontinued the core phase treatment • Reason for discontinuation | The number of subjects in Safety Set of Core Phase |

Extension Phase

| Items | The denominator of percentage |
|--|---|
| 
 • Entered the Extension Phase • Treated with study drug • Not treated with study drug • Completed study • Discontinued the study • Reasons for discontinuation of study | The number of subjects in Safety Set of Extension Phase |

| | |
|---|--|
| 
 • Ongoing in the extension phase • Completed the treatment • Discontinued the treatment • Reasons for discontinuation of treatment | |
|---|--|

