11.3.9 Subjects with any Rescue Therapy Use

Population: Full Analysis Set, Per Protocol Set (for Core Phase only)

Target Phases: Core Phase, Extension Phase

Analysis items: - Rescue therapy (Yes/No)

Contents: - The number of subjects with rescue therapy (Yes/ No) and its proportion with 95% CI are calculated.

Definitions: - Rescue therapy (Yes): The number of subjects who use at least one rescue therapy after the first administration of study drug in each phase (Core Phase (26-week treatment period) or Extension Phase).

- If one subject takes the same therapy in both Core Phase and Extension Phase (e.g. the end date of rescue therapy in Core Phase is ongoing), that subject will be counted in Core Phase and Extension Phase respectively.
- The denominator to calculate the proportion is the target population (the number of subjects in Full Analysis Set/Per Protocol Set)
- Rescue therapy will be defined as the addition of any new ITP medication or medication to treat thrombocytopenia (examples below). TPO receptor agonists are not allowed as rescue therapy.

- Corticosteroids (ATC level 2 = “CORTICOSTEROIDS FOR SYSTEMIC USE”)
- Intravenous immunoglobulin (IVIg) therapy (ATC level 2= “IMMUNE SERA AND IMMUNOGLOBULINS”)
- Anti-D therapy (PT = “Anti-D (rh) immunoglobulin”)
- Mycophenolate mofetil (PT = “Mycophenolate mofetil”)
- Azathioprine (PT = “Azathioprine”)
- Danazol (PT = “Danazol”)
- Cyclosporin A (PT = “Ciclosporin”)
- Platelet transfusion (concomitant procedure as “TRANSFUSIONS”)
- Any increase in baseline dose of a concomitant ITP medication
- Regarding 95% CI for binomial proportions, refer to [8.3.2 Proportion and Confidence Intervals for proportions.](#)

11.3.10 Subjects with a Reduction/Discontinuation in use of Concomitant ITP Medications from Baseline

Population: Full Analysis Set, Per Protocol Set

Target Phases: Core Phase

Analysis items: - Reduction in use of concomitant ITP medications

- Discontinuation in use of concomitant ITP medications

Contents: - Calculate the number of subjects who have a reduction/discontinuation of Concomitant ITP medications after baseline.

For each item, the denominator is as below

| Items | The denominator of percentage |
|--|---|
| 
 • Reduction of Concomitant ITP medications after baseline • Discontinuation of Concomitant ITP medications after baseline | The number of subjects who used concomitant ITP medications at baseline |

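### TEAE, rescue and bleeding results are crude proportions with no time-at-risk measure, so they cannot be compared between the 26-week Core Phase and the open-ended Extension, or between data cuts

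*SAP*

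**What the plan says.** **TEAEs and AESIs.** SAP 13.2.1 sets "Target Phases: Core Phase, Core Phase and Extension Phase", and 13.2.4 does the same for AESIs. Neither has an Extension-only column. The measure in 13.2.1 is: "The number of events and the number and proportion of subjects who experienced at least 1 event in the Analysis items are calculated". The denominator is a number of subjects: "The denominator to calculate the proportion is the target population".

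**Rescue.** SAP 11.3.9 reports Core and Extension separately and counts subjects "who use at least one rescue therapy after the first administration of study drug in each phase", over the number in the FAS or PPS.

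**Bleeding.** SAP 11.3.11 gives the worst post-baseline WHO grade for each phase, over the number in the analysis population. The Extension window runs from Month 1 to each subject's last visit, so its length varies.

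**Length of observation.** The Core treatment period is 26 weeks. In the Extension, subjects "can continue to receive avatrombopag in the Extension Phase until market authorization in Japan" (Protocol 4.4). Protocol 7.3.1 schedules monthly visits and allows them to go on past Month 23.

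**Data cuts.** SAP 5.4 plans one analysis after the last patient completes Core and another after the last completes the Extension. In SAP 9.2, the row for subjects still in the Extension "only exists in the first analysis (after the last patient completes the Core Phase".

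**Exposure.** SAP 13.1 summarises treatment duration but never uses it as a denominator. SAP 13.2.8 tabulates TEAEs by onset interval and PT, again over the whole target population. No person-time rate, at-risk denominator or time-to-event estimate is specified for TEAEs, rescue or bleeding.

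**The concern.** The primary objective of the Extension is long-term safety and tolerability (SAP 3.2.1). Its secondary objective includes bleeding and rescue use (SAP 3.2.2). Both invite the question whether risk stays level, rises or falls with longer treatment.

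A proportion of subjects with at least one event depends on how long they were watched. For a fixed set of subjects, the pooled TEAE proportion can stay level or rise as follow-up lengthens; it can never fall. A higher figure for Core plus Extension than for Core is therefore expected even at constant risk.

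Rescue and bleeding are not pooled, so the problem there differs. Core and Extension are unequal in length, and at the first analysis a subject with a few weeks of Extension counts in the denominator the same as one with a year. Setting that Extension proportion beside the Core proportion, or beside the final Extension proportion, compares unequal periods.

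**Working it through.** The documents state no event rate or incidence for these outcomes, so there is no plan figure to reproduce. The check asks how far a crude proportion moves when only follow-up changes.

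**Inputs from the documents:** Core 26 weeks; Extension 24 scheduled months, taken as 104 weeks, so 26 + 104 = 130 weeks in all (the SAP 13.1 exposure categories reach 126 weeks or more); about 19 subjects.

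**Assumptions:** constant hazard, no dropout, and a 26-week risk p of 5% to 30%.

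**Pooled Core plus Extension (TEAEs, AESIs).** The hazard is λ = −ln(1 − p)/26 per week. The proportion at T weeks is 1 − exp(−λT), which at 130 weeks equals 1 − (1 − p)^5. For p = 10%: 1 − 0.9^5 = 41.0%. The rate per 100 patient-years is λ × 52.18 × 100.

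| Assumed 26-week risk | Proportion at 130 weeks | Ratio | Affected of 19, 26 vs 130 weeks | First events per 100 patient-years |
|---|---|---|---|---|
| 5% | 22.6% | 4.5 | 1.0 vs 4.3 | 10.3 |
| 10% | 41.0% | 4.1 | 1.9 vs 7.8 | 21.1 |
| 20% | 67.2% | 3.4 | 3.8 vs 12.8 | 44.8 |
| 30% | 83.2% | 2.8 | 5.7 vs 15.8 | 71.6 |

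Under this model the rate in the last column is the same at either time. The ratio shrinks as the outcome becomes more frequent: at an assumed 26-week risk of 85% it cannot exceed 1/0.85 = 1.18. The row for any TEAE may be of that kind.

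**Extension only, at Core lock (rescue, bleeding).** Assume entrants' Extension time at the cut is uniform on 0 to A weeks. The expected proportion is 1 − [1 − exp(−λA)]/(λA). For p = 10% and A = 52: λA = 0.2107, and 1 − 0.190/0.2107 = 9.8%.

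| Assumed 26-week risk | Core lock, A = 26 | A = 52 | A = 78 | After a full 104 weeks |
|---|---|---|---|---|
| 5% | 2.5% | 5.0% | 7.3% | 18.5% |
| 10% | 5.1% | 9.8% | 14.3% | 34.4% |
| 20% | 10.4% | 19.3% | 27.1% | 59.0% |
| 30% | 15.9% | 28.5% | 38.6% | 76.0% |

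With the same hazard throughout, the Extension figure at Core lock can fall below, near or above the Core figure, depending only on how long subjects have been in the Extension.

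**The case against.** **The SAP already lets a reader judge TEAE risk over time.** It reports event counts (13.2.1), treatment duration with numbers reaching set durations (13.1) and TEAEs by onset interval (13.2.8). This stands in part. A reader might infer that nothing in the plan speaks to change in TEAE risk with time; that is too strong. But the onset table keeps the full denominator in late intervals, whoever is still observed, and the SAP does not combine counts and duration into a rate. For rescue and WHO grade there are only individual listings.

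**A Core-lock proportion is not wrong.** This stands. A reader might infer that Extension rescue and bleeding are biased downwards at that cut. They are low only relative to a completed Extension. The SAP does not present them as long-term risk, and it shows who is still ongoing. The Extension FAS also contains entrants only (SAP 7.2), so the denominator is not padded with subjects who never entered.

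**A rate is no cure.** This also stands. It is stable over follow-up only if the hazard is constant. Core includes titration and reduction of concomitant ITP medication. Extension entrants must have no significant safety or tolerability concern (Protocol 5.1.2), and subjects with poor response or repeated rescue may have stopped earlier (Protocol 5.3.1). Core and Extension rates can differ for those reasons alone.

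**Precision is poor.** True. Nineteen subjects for 26 weeks give 19 × 0.5 = 9.5 patient-years. Three events are then about 32 per 100 patient-years, with an exact 95% interval of about 6.5 to 92. That is a reason to print the interval; it does not make proportions over unequal periods comparable.

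**Conclusion.** The point holds as a limit on interpretation. The crude proportions are correct for the time observed, but none of the planned summaries of TEAEs, AESIs, rescue or WHO grade puts events over time at risk, so they do not support statements across phases or data cuts.

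The size depends on assumptions outside the documents. For pooled TEAEs and AESIs it is 4.5- down to 2.8-fold for assumed 26-week risks of 5% to 30%, under constant hazard and full follow-up to 130 weeks. Dropout or earlier authorization would shorten follow-up and shrink it, and for very frequent outcomes it approaches 1. A reader might infer that every safety figure is inflated about fourfold, or that rescue and bleeding are pooled across phases; the documents support neither.

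The primary and key secondary endpoints are unaffected, and no formal cross-phase comparison is planned. This is a cheap improvement that helps the Extension answer its own primary question.

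**What to change.** Keep all the crude proportions, and add:

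- **SAP 13.2.1 and 13.2.4:** subjects with a first event per 100 patient-years, for Core, Extension and Core plus Extension.
- **SAP 11.3.9 and 11.3.11:** the same by phase; for bleeding, by the WHO grades already tabulated.
- **Beside each rate:** total and median follow-up and an exact 95% CI.
- **Time at risk:** time to first event, or to end of phase or data cut if there is none. The text must state where the TEAE window closes, because the SAP gives no end and subjects who do not enter the Extension have taper and follow-up visits to Week 34. It must name the analysis set for the pooled tables, because SAP 7.4 defines Core and Extension Safety Sets but no combined one. It must also say how rescue continuing from Core into the Extension is handled, since 11.3.9 counts such a subject in both phases.
- **Interpretation:** one sentence saying that any cross-phase difference is descriptive, because Extension entrants are selected and hazards may not be constant.

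The planned analyses already use the dates needed, so no new data collection is required. The cost is a few columns, a short definition and wide intervals at about 19 subjects.
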